## 6.2.4 Precautions and warnings for the investigator

Only precautions and warnings that require a study-specific action during the investigation are listed below. For the complete list of precautions and warnings please refer to current IB [46] (section 8.1.5) for saypha® VOLUME Lidocaine and to the respective IFU of the comparator device.[14]

Each treating investigator has to familiarize himself / herself with the CIP and the detailed precautions and warnings in the above-mentioned documents.

# 6.2.4.1 saypha® VOLUME Lidocaine

#### Precautions and Warnings

• According to the IB (section 8.1.5), sensitive skin may be pre-treated using a local anesthetic patch or cream (also see section 6.2.2).

**Note:** Whenever possible (i.e., if the subject agrees) additional topical anesthetic (patch or cream) should be avoided in this investigation to not falsify the pain assessment (see section 6.4.14). In case additional local anesthesia is used, this has to be documented as concomitant treatment in the subject's records and the eCRF.

- The device must not be used if the expiry date has lapsed, or if the integrity of the syringe cannot be verified, of if packaging or contents are damaged (open or shifted tip cap or in an opened or damaged blister, syringe is not stored in its originally sealed blister, needle with a damaged container). In such case follow instructions given in section 14.9.
- The device should only be used with the needles / cannulas and syringe provided by the manufacturer / sponsor's representative (also see section 2.1 and section 6.4.19).
- Do not inject into blood vessels, bones, tendons, ligaments, nerves or muscles. Do not inject the device into naevi. In such cases, subjects should receive prompt medical attention and possibly evaluation by an appropriate health care practitioner specialist should an intravascular injection occur. Also see section 6.2.5 and section 14 for documentation and reporting obligations for AEs. Also see sections 6.3.6, 14.5.4 and 16.1.
- Subjects should be advised not to apply make-up for twelve hours after injection and to avoid prolonged exposure to sunlight and UV; also subjects should not use saunas or Turkish baths for one Week after the injection (also see section 6.3.8).
- Subjects should be advised not to massage the treatment site for a few days following the injection, to avoid the possible risk of product mobility (also see section 6.3.8).
- The device should never be placed in contact with quaternary ammonium compounds (such as benzalkonium chloride solutions) or with medical-surgical instruments that have been in contact with these substances (also see section 4.3).

## 6.2.4.2

### Warnings

• The product must not be injected into blood vessels. Introduction of **sector** into the vasculature may lead to embolization, occlusion of the vessels, ischemia, or infarction. Take extra care when injecting soft tissue fillers, for example, after insertion of the needle, and just before injection, the plunger rod can be withdrawn slightly to aspirate and verify the needle is not intravascular, inject the product slowly and apply the least amount of pressure necessary.

Rare but serious adverse events associated with the intravascular injection of soft tissue fillers in the face have been reported and include temporary or permanent vision impairment, blindness, cerebral ischemia or cerebral hemorrhage, leading to stroke, skin necrosis, and damage to underlying facial structures. Immediately stop the injection if a subject exhibits any of the following symptoms, including changes in vision, signs of a stroke, blanching of the skin, or unusual pain during or shortly after the procedure (see section 6.4.8 for information on visual examinations to be performed).

Subjects should receive prompt medical attention and possibly evaluation by an appropriate health care practitioner specialist should an intravascular injection occur. Also see section 6.2.5 and section 14 for documentation and reporting obligations for AEs. Also see sections 6.3.6, 14.5.4 and 16.1.

- Product use at specific sites in which an active inflammatory process (skin eruptions such as cysts, pimples, rashes, or hives) or infection is present should be deferred until the underlying process has been controlled. The treating investigator must document subject's temporary discontinuation and the reason in the subject's source records and on the electronic Case Report Form (eCRF).
- Treatment site reactions consist mainly of short-term inflammatory symptoms and generally resolve within 2 to 4 weeks (also see section 4.2.2).

## Precautions

- is packaged for single-patient use. Do not resterilize. Do not use if package is open or damaged. In such case follow instructions given in section 14.9.
- injectable gel is a clear, colorless gel without particulates. In the event that the content of a syringe shows signs of separation and/or appears cloudy, do not use the syringe. In such case follow instructions given in section 14.9.
- Directions for Use may adversely impact the sterility, homogeneity, and performance of the product. In such case follow instructions given in section 14.9.
- As with all transcutaneous procedures, dermal filler implantation carries a risk of infection. Standard precautions associated with injectable materials should be followed.
- The safety has been established for use in patients between 35 and 65 years of age for cheek augmentation. However, the filler is indicated for cheek augmentation to correct age related volume deficit in the midface in adults over the age of 21 (see InC#1 in section 6.3.3.1).
- Subjects may experience late onset nodules with use of dermal fillers, including (see section 14 for documentation and reporting obligations for AEs).
- Subjects who experience skin injury near the site of the section of the section of the section may be at a higher risk for adverse events (see section 14 for documentation and reporting obligations for AEs).
- The safety of **sector** with cannula for cheek augmentation has not been established in subjects with Fitzpatrick Skin Types V and VI. However, for this study, inclusion of subjects with Fitzpatrick Skin Types IV to VI is encouraged (see section 6.6).

#### 6.2.5 Rescue medication and emergency plan

In case of any expected adverse event associated with the study treatment (e.g., vascular occlusion), the Expert Consensus Recommendations for treatment of Soft Tissue Filler Complications [42] or the ASDS guidelines of care: injectable fillers [43] should be followed in the discretion of the investigator. Both references are filed in the Investigator Site File.

The investigation sites will be required to have an emergency plan in place and a minimum medication readily available in case a suspected vascular occlusion or allergic reaction occurs. CRAs will control, if such an emergency plan is in place and the medication is available.

Any rescue medication / procedure applied should be documented in the subject's source record and in the eCRF as concomitant treatment (see section 6.4.5).

#### 6.2.6 Device accountability

Both devices (saypha® VOLUME Lidocaine and the context of this clinical investigation plan (CIP).

The devices must be handled in accordance with the sponsor's instructions (see section 6.2.1 to 6.2.4) and the current version of the IB of the test device [46] and the IFU of the comparator device [14], respectively.

Documentation of receipt, dispensing/use in individual subjects, and return of device must be maintained by the investigator or his/her designee. Appropriate forms will be provided by the sponsor or their representative to facilitate device accountability.

At the end of the investigation, all remaining clinical investigation material should be destroyed on site, following the site-specific destruction procedure after a monitor has verified all accountability documentation. If the site does not have an appropriate destruction process, the material must be returned to the sponsor designee.

Empty or used syringes will not be returned to the sponsor, but will be destroyed by the investigation site, in line with their routine procedure for medical waste disposal. Used needles/cannulas should be disposed immediately after the use as per routine procedure for medical waste disposal at the site.

According to the underlying monitoring plan (see also section 6.7) the monitor will regularly check study documentation and inventory of devices held by the investigator to verify accountability of all devices used.

## 6.2.7 Handling of deficient devices

Any device alleged to be deficient must not be used by the investigator and must be returned to the sponsor's designee. In case of device deficiencies also instructions in section 14.9 must be followed.

## 6.3 Subjects

## 6.3.1 Number of subjects and duration of the clinical investigation

Up to 486 subjects are planned to be randomized in a 2:1 ratio (test device: 324, comparator device: 162) and treated. Approximately 516 subjects will need to be screened to reach 486 subjects randomized (accounting for a screening failure rate of approx. 6%) and to ensure that 437 subjects will be evaluable for the primary endpoint. Approximately 300 subjects are estimated to qualify for repeat treatment.

Inclusion of subjects is planned to be as equally distributed as possible between the sites. The clinical investigation is planned to be conducted at approximately 16 study sites with enrolment target of approximately 20 to 30 subjects per site. The maximum expected number of subjects to be enrolled per each site will be 45 but may be higher if agreed with the Sponsor.

Each subject will take part in the investigation for up to 92 weeks.

The total anticipated duration of the investigation, from the first-subject-first visit to the last-subject-lastvisit, is around 114 weeks, based on expected recruitment period of about 22 weeks.

## 6.3.2 *Recruitment strategy*

Subjects will be recruited by sites located in the USA (a list of the sites, including names, addresses and positions of the corresponding Principal Investigators, is kept separately from the CIP).

The investigator may also offer participation in the study to potential candidates identified in their subject database. The investigation may be advertised as requested by the sites. In such case, the advertising strategy and materials will be submitted to the Institutional Review Board (IRB) / Ethics Committee (EC)for prior review and approval.

Every effort will be made to include individuals with all Fitzpatrick skin types (FST, see section 6.4.2 for details) in a proportional pattern adequately include patients of diverse skin colcor and background in this study.

The FST enrollment levels planned to be achieved are as follows:

- **FST I to III:** approximately 80% of subjects
- FST IV to VI: at least 20% of subjects
- **FST V and VI:** approximately 10% of subjects

These FST enrollment levels will not be seen in each investigation site, i.e., there will be overrepresentation at some sites and underrepresentation at other sites. However, enrollment of the different FST levels will be monitored during the enrollment period via the eCRF system (report) by the project management team at the CRO. Details how to monitor enrollment levels via the eCRF system will be described in the project management plan.

# 6.3.3 Eligibility criteria – Baseline treatment

# 6.3.3.1 Inclusion criteria

A subject must meet **ALL** of the following criteria to be **ELIGIBLE** for the study:

- 1. Male or female subjects aged 22 75 years (inclusive) of age at Screening
- 2. Subjects with bilateral, approximately symmetric moderate to severe midface volume deficit (severity scores of 2 or 3 on the 5-point Midface Volume Deficit Severity Scale), as assessed by the blinded evaluator at the site
- Females of childbearing potentialD must have a negative urine pregnancy test and must agree to use an effectiveE method of birth control throughout the entire study
   Male subjects with female pertners of shild bearing potential must agree to use controportion

Male subjects with female partners of child-bearing potential must agree to use contraception throughout the entire study (surgical sterilization or a physical barrier such as a condom).

- 4. Healthy skin in the midface area and free of diseases that could interfere in cutaneous aging evaluation
- 5. Willingness to abstain from any aesthetic or surgical procedures in the treatment area for the duration of the entire investigation, including botulinum toxin injection (except glabella or forehead botulinum toxin treatment)
- 6. Subjects who understand the purpose and conduct of the study and having given written informed consent and are willing and able to attend the study visits as judged by the investigator

# 6.3.3.2 Exclusion criteria

A subject who meets **ANY** of the following criteria is **NOT** eligible for the study and must not be enrolled:

- 1. Females, who are pregnant and/or, lactating or planning to become pregnant during the clinical investigation
- 2. History of severe allergies manifested by a history of anaphylaxis or history or presence of multiple severe allergies
- 3. History of hypersensitivity to hyaluronic acid preparations, lidocaine or any amide-based anesthetic
- 4. Tendency to keloid formation and/or hypertrophic scars and/ or have pigment disorders
- 5. Known human immune deficiency virus-positive individuals
- 6. Presence of infectious, inflammatory or proliferative cancerous or pre-cancerous lesions in the treatment area
- 7. Re-current (three times a year over the last year) herpes simplex in the treatment area
- 8. History or presence of any autoimmune or connective tissue disease, or current treatment with immuno-modulating therapy
- 9. Uncontrolled (or unstable) Diabetes mellitus or systemic diseases as per investigator discretion

<sup>D A woman is considered to be of childbearing potential (WOCBP) if fertile, following menarche and until becoming postmenopausal unless permanently sterile. Permanent sterilization methods include hysterectomy, bilateral salpingectomy and bilateral oophorectomy. A postmenopausal state is defined as no menses for 12 months without an alternative medical cause.

<sup>E Effective methods of birth control include: combined (estrogen and progestogen containing) hormonal contraception associated with inhibition of ovulation (oral, intravaginal, transdermal), progestogen-only hormonal contraception associated with inhibition of ovulation (oral, injectable, implantable), intrauterine device (IUD), intrauterine hormone-releasing system (IUS), bilateral tubal occlusion), vasectomized partner (provided that is the sole sexual partner of the subject and that the vasectomized partner has received medical assessment of the surgical success) and sexual abstinence (if in line with the preferred and usual lifestyle of the subject and defined as refraining from heterosexual intercourse during the entire period of the trial).

- Previous facial plastic surgery, tissue augmentation with silicone, fat or another non-absorbable substance (permanent fillers) and semi-permanent / long-lasting fillers (e.g., *poly-L-lactic* acid (PLLA), Polymethylmethacrylate (PMMA) filler) in the area of device application and during the entire investigation
- 11. Implantation of dermal fillers in the treatment area within the preceding 24 months prior to Visit 1 (Screening) and during the entire investigation
- 12. Subject has received any of the following aesthetic treatments in the midface area: e.g., laser therapy, absorbable and non-absorbable sutures (threads), dermabrasion, mesotherapy, micro-needling and/or botulinum toxin (including treatment of crow's feet in the outer eye region) within the last 12 months prior to Visit 1, chemical peeling within the last three months prior to Visit 1 or is planning to undergo such procedures during entire investigation
- 13. Facial lipolysis, including submental fat treatments, within the previous 12 months prior to Visit 1 (Screening) and during the entire investigation
- 14. Bariatric surgery within 12 months prior to Visit 1 (Screening) and during the entire investigation
- 15. History of bleeding disorder and/or use of anticoagulant, antiplatelet, thrombolytic medication, anti-inflammatory drugs (oral/injectable corticosteroids or non-steroidal anti-inflammatory drugs, e.g., or other substances known to increase coagulation time (vitamins or herbal supplements, e.g., St. John's Wort, high doses of vitamin E supplements) from ten days pre- to seven days post injection (baseline treatment and touch-up treatment)
- Planned dental/oral surgery or modification (bridge-work, implants) within four weeks prior to each injection and to a minimum of four weeks post injection (baseline treatment and touch-up treatment)
- 17. Beard longer than three-day beard, or excessive facial hair that could interfere in evaluation of treatment as judged by the investigator
- 18. Subjects who have one of the following assessments during the visual examinations at Visit 2 (Baseline): Snellen visual acuity test worse than 20/40 (with corrective eyewear, if applicable), abnormal confrontational visual field test, or abnormal ocular motility test.
- 19. Subjects with active COVID-19 infection and subjects with symptoms consistent with COVID-19 infection including any other respiratory symptoms/illnesses within the past 14 days unless tested negative prior to Visit 1 (Screening)
- 20. Any medical condition prohibiting the inclusion in the study according to the judgment of the treating investigator
- 21. Previous enrollment in this clinical investigation
- 22. Current participation in another clinical trial, or treatment with any investigational drug/medical device within 30 days prior to Visit 1 (Screening) or within five half-lives of an investigational drug, whichever is longer and during the entire investigation
- 23. Midface volume deficit due to a congenital defect, trauma, or abnormalities in facial adipose tissue distribution such as those associated with HIV related lipodystrophy
- 24. Subjects who experienced weight loss for a minimum of 10% over the last 12 months (e.g., post bariatric patients), or subjects who have the intention to change eating habits that result in a weight gain or loss >10% during the entire investigation
- 25. Any individual whose willingness to volunteer in this clinical investigation could be unduly influenced by the expectation, whether justified or not, of benefits associated with participation or of retaliatory response from senior members of a hierarchy in case of refusal to participate (e.g., persons with a legal custodian appointed due to mental disability, prisoners, soldiers and other members of the armed forces, civil servants).
- 26. Close affiliation with the investigator (e.g., a close relative, financially dependent on the study site) or subject who is an employee of the sponsor's company or group companies of the sponsor.

# 6.3.4 Eligibility criteria – Touch-up treatments (TUP1 and TUP2)

# 6.3.4.1 Inclusion Criteria

A subject must meet **ALL** of the following criteria to be **ELIGIBLE** for each **touch-up-treatment**:

1. Females of childbearing potential must have a negative urine pregnancy test

# 6.3.4.2 Exclusion criteria

A subject who meets **ANY** of the following criteria is **NOT** eligible for each **touch-up treatment**:

- 1. Occurrence of a related Serious Adverse Event or Adverse Event of Special Interest (i.e., embolic events, with possible, probable, or causal relationship to an intravascular injection of the device, as changes in vision [loss of vision, blurriness, double vision, pain in or around the eye, blindness, blind spots, problems moving the eyes], skin changing color around the eyelids or around the site of injection, other embolic phenomenon, e.g., stroke, skin necrosis, or impending necrosis) during or after the previous injections
- 2. Subjects who experienced visual changes considered abnormal clinically significant or other serious medical conditions during or after the previous injections
- 3. Subjects who have one of the following assessments during the visual examinations: Snellen acuity test worse than 20/40 (with corrective eyewear, if applicable), abnormal confrontational visual field test, or abnormal ocular motility test.

# 6.3.5 Eligibility criteria – Repeat-treatment (with saypha® VOLUME Lidocaine only)

The eligibility criteria given in section 6.3.5.1 and section 6.3.5.2 must be assessed for repeat-treatment.

## 6.3.5.1 Inclusion criteria

A subject must meet ALL of the following criteria to be ELIGIBLE for repeat-treatment:

- Subjects with bilateral, approximately symmetric moderate to severe midface volume deficit (severity scores of 2 or 3 on the 5-point MVDSS), as assessed by the blinded evaluator at the site. The subject does not have to return to his baseline severity to be permitted to receive a repeattreatment.
- 2. Subject has completed initial treatment phase up to Visit 9 (SV1) and is willing to attend the study visits of the screening phase for repeat-treatment and repeat-treatment phase
- 3. Females of childbearing potential must have a negative urine pregnancy test
- 4. Healthy skin in the midface area and free of diseases that could interfere in cutaneous aging evaluation

## 6.3.5.2 Exclusion criteria

Subjects who meet **ANY** of the following criteria are **NOT** eligible for **repeat-treatment**:

- Occurrence of a related Serious Adverse Event or Adverse Event of Special Interest (i.e., embolic events with possible, probable, or causal relationship to an intravascular injection of the device, as changes in vision [loss of vision, blurriness, double vision, pain in or around the eye, blindness, blind spots, problems moving the eyes], skin changing color around the eyelids or around the site of injection, other embolic phenomenon, e.g., stroke, skin necrosis, or impending necrosis) during or after the baseline injection and/or touch-up injections
- 2. Occurrence of a related Adverse Event that occurred during the initial treatment phase, and is ongoing at the time of the repeat treatment (i.e., relationship is classified as "possible", "probable" or "causal relationship"; outcome is "not recovered / resolved", "recovering / resolving", "recovered / resolved with sequelae" or "unknown")
- 3. Subjects who experienced visual changes considered abnormal clinically significant or other serious medical conditions during or after the baseline or touch-up injections, respectively

- 4. Subjects who have one of the following assessments during the visual examinations: Snellen acuity test worse than 20/40 (with corrective eyewear, if applicable), abnormal confrontational visual field test, or abnormal ocular motility test
- 5. Subjects who became pregnant since start of the study or planning to become pregnant during the clinical investigation
- 6. Known human immune deficiency virus-positive individuals
- 7. Presence of infectious, inflammatory or proliferative cancerous or pre-cancerous lesions in the treatment area
- 8. Development of re-current (three times a year over the last year) herpes simplex in the treatment area since study start
- 9. Development of any autoimmune or connective tissue disease since study start, or current treatment with immuno-modulating therapy
- 10. Development of uncontrolled (or unstable) diabetes mellitus or systemic diseases since study start as per investigator discretion
- 11. Facial plastic surgery, tissue augmentation with silicone, fat or another non-absorbable substance (permanent fillers) and semi-permanent fillers (e.g., *poly-L-lactic* acid) in the area of device application and during the initial treatment phase of the investigation
- 12. Implantation of dermal fillers (other than the test and comparator device used in the investigation) in the treatment area during the initial treatment phase of the investigation
- 13. Subject has received any of the following aesthetic treatments in the midface area: e.g., laser therapy, absorbable and non-absorbable sutures (threads), dermabrasion, mesotherapy, microneedling and/or botulinum toxin (including treatment of crow's feet in the outer eye region), or chemical peeling during the initial treatment phase of the investigation or is planning to undergo such procedures during the repeat-treatment phase of the investigation
- 14. Facial lipolysis, including submental fat treatments during the initial treatment phase of the investigation
- 15. Bariatric surgery during the initial treatment phase of the investigation
- 16. Development of bleeding disorder and/or use of anticoagulant, antiplatelet, thrombolytic medication, or anti-inflammatory drugs (oral/injectable corticosteroids or non-steroidal anti-inflammatory drugs, e.g., **Sector 2019**) or other substances known to increase coagulation time (vitamins or herbal supplements, e.g., St. John's Wort, high doses of vitamin E supplements) from ten days pre- to seven days post injection (repeat-treatment and touch-up treatment)
- 17. Planned dental/oral surgery or modification (bridge-work, implants) within four weeks prior to the injection and to a minimum of four weeks post injection
- 18. Beard longer than three-day beard, or excessive facial hair that could interfere in evaluation of treatment as judged by the investigator
- 19. Any medical condition prohibiting the inclusion for repeat-treatment according to the judgement of the treating investigator
- 20. Previous enrollment in initial treatment phase of this clinical investigation and early termination, or significant incompliance with the protocol requirements
- 21. Current or previous treatment with another investigational drug and/or medical device or participation in another clinical study
- 22. Midface volume deficit due to a trauma, or abnormalities in facial adipose tissue distribution such as those associated with HIV related lipodystrophy
- 23. Subjects who experienced weight change for a minimum of 10% since study start or subjects who have the intention to change eating habits that result in a weight gain or loss >10% during the entire investigation
- 24. Subjects with active COVID-19 infection and subjects with symptoms consistent with COVID-19 infection including any other respiratory symptoms/illnesses within the past 14 days unless tested negative prior to Visit RT1

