---------------------------------------------------------------------	---------------------------------------------------------------------------------------------------------------------------------------------------------------------------------------------------------------------------------------------------------------------------------------------------------------------------------------------------------------------------	--	
Source Records	Collection of source documents containing source data.		
Sponsor	Is an individual, company, institution or organization taking responsibility and liability for the initiation and management of a clinical investigation, and arranging the financial setup.		
Subject	Is an individual who is or becomes a participant in a clinical investigation either as a recipient of the test device or the comparator device.		
Treatment (phase) (study-specific definition)	Baseline treatment: Treatment at Visit 2 is defined as "baseline treatment";		
	Touch-up treatment 1: Optional treatment at Visit 3 is defined as "touch-up treatment 1" (TUP1)		
	Initial treatment (phase): Baseline treatment and touch-up treatment together are defined as "initial treatment"; The study phase between Baseline visit and Visit 9 (SV1) is defined as initial treatment phase.		
	For initial treatment either saypha® VOLUME Lidocaine (test device) or the comparator device and the subject are administered (according to randomization of the subject)		
	Repeat-treatment (phase): Optional treatment (with saypha® VOLUME Lidocaine only) at Visit RT1 is defined as "repeat-treatment". The study phase beginning with repeat-treatment at Visit RT1 and up to Visit RT5 is defined as repeat-treatment phase.		
	Touch-up treatment 2: Optional treatment at Visit RT2 is defined as "touch-up treatment 2" (TUP2)		
	For repeat-treatment only saypha® VOLUME Lidocaine (test device) is administered.		
Treating (unblinded) investigator (study-specific definition)	Responsible for all study related assessments and procedures (except those allocated to the blinded evaluator at the site and the central independent blinded photographic reviewer).		
Trial Master File (TMF)	Binder(s) maintained at the sponsor's (CRO's) office containing all regulatory and study specific documents including the essential documents according to the ISO-GCP Guideline.		

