## 14.3 AE/SAE documentation

For each AE the following must be reported:

- Description of the event (event term)
- Seriousness
- Start date
- Intensity
- Action taken with subject (none, medical and/or surgical / non-pharmaceutical procedure)
- Action taken with device (none [no action taken], device withdrawn [no touch-up treatment(s) / repeat-treatment due to AE], device interrupted [touch-up treatment(s) / repeat-treatment later than required by study design due to AE or injection interrupted due to AE during treatment session])
- Outcome
- End date (if applicable)
- The relationship to the device and procedure, respectively

The information will be documented in subject's source record and in the eCRF.

Each AE and any new information concerning these events has to be documented, even if the investigator feels that it is not connected with the device or procedure.

The AE will be described in precise, standard medical terminology. The investigator will attempt to establish a diagnosis of the event based on signs, symptoms, and/or other clinical information (including affected body site(s)). In such cases, the diagnosis will be documented as the AE and not the individual

signs/symptoms. In case of any injection site reaction the exact location (e.g., upper or lower lips) should be clearly noted.

Each AE should be reported separately. The investigator will record all AEs in subject's (medical) record and on the "Adverse Events" page of the eCRF. For SAEs, the "Serious Adverse Event Reporting Form" must also be completed. Complete description of all AEs should be also available in source documents of the subject.

Adverse events will be documented beginning after provision of informed consent until the last visit of the subject. The follow-up period will be prolonged outside the investigation, if a related AE is ongoing and not stabilized after 24 weeks after last injection of the repeat-treatment phase (see section 14.6 for details).

AEs initially observed during or after baseline treatment are defined as treatment-emergent AEs (TEAEs). AEs occurring after informed consent but before baseline treatment will be defined as non-TEAEs. Any medical condition that is present prior to day of screening should be considered as medical history (i.e., concomitant disease) and not recorded as an AE. If such condition, however, deteriorates after the device administration, at any time during the investigation, it should be reported as an AE.

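### The mandatory bar on repeat treatment for an ongoing related adverse event looks back only to Visit 9 and misses events that start between Visit 9 and RT1

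*Protocol*

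**What the plan says.** Criterion 2 of Protocol 6.3.5.2, repeated in the synopsis, excludes a subject from repeat treatment for "Occurrence of a related Adverse Event that occurred during the initial treatment phase, and is ongoing at the time of the repeat treatment". It then specifies that the relationship may be possible, probable or causal. The qualifying outcomes include events that are still resolving, have left sequelae or have an unknown outcome.

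The Glossary fixes the phases. For the first: "The study phase between Baseline visit and Visit 9 (SV1) is defined as initial treatment phase". For the second: "The study phase beginning with repeat-treatment at Visit RT1 and up to Visit RT5 is defined as repeat-treatment phase". Inclusion criterion 2 in 6.3.5.1 names the stage between them on its own, since the subject must be "willing to attend the study visits of the screening phase for repeat-treatment and repeat-treatment phase". Section 6.3.11 groups this screening stage with repeat treatment, and 6.5.16 gives it its own early-termination rule.

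The neighbouring safety criteria use a different look-back. Criterion 1 (related serious events and events of special interest) applies "during or after the baseline injection and/or touch-up injections". Criterion 3 (significant visual changes and other serious conditions) applies "during or after the baseline or touch-up injections, respectively". Neither stops at Visit 9.

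**The concern.** The rule is strict about which ongoing related events bar re-injection, but it ties the bar to a phase that ends before the decision is made. Two subjects with the same ongoing related event at RT1, for example a non-inflammatory nodule or an induration, get different mandatory results depending only on whether it began before or after Visit 9. The later event is the newer and less well characterised of the two, and it is the one that escapes the rule. No reason is given for a shorter look-back in criterion 2 than in criteria 1 and 3.

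At stake is subject safety at re-injection. There is also a slight effect on the descriptive safety results of the repeat-treatment phase, including the cross-over group, because an event already present at RT1 can be carried into it.

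**Working it through.** **Length of the uncovered interval.** Inputs: SV2, SV3 and SV4 fall 4, 8 and 12 weeks after Visit 9, each ±7 days (Table 2); RT1 may follow the qualifying screening visit by up to 14 days or be combined with it (Table 3 footnotes). The interval from Visit 9 to RT1 is the qualifying visit's offset plus 0 to 2 weeks.

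| Qualifying visit | Nominal (weeks) | With ±1 week visit window |
|---|---|---|
| Visit 9 | 0 to 2 | 0 to 2 |
| SV2 | 4 to 4 + 2 = 6 | 3 to 7 |
| SV3 | 8 to 8 + 2 = 10 | 7 to 11 |
| SV4 | 12 to 12 + 2 = 14 | 11 to 15 |

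**Check against a stated figure.** Section 6.3.1 gives a maximum participation of 92 weeks. Adding the schedule: 2 (screening) + 2 (to touch-up 1) + 48 (to Visit 9) + 12 (to SV4) + 2 (to RT1) + 2 (to touch-up 2) + 24 (to RT5) = 92. The figure is reproduced with 12 + 2 = 14 weeks between Visit 9 and RT1. The heading of 6.5.10 puts RT1 at most 12 weeks ±7 days after Visit 9. That would give a total of 90 weeks, or 91 with the window, so the 92-week figure supports 14.

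**When the missed events would start.** Counted from the last injection, onset lies between Week 48 and Week 48 + 14 = 62 nominally. With windows it lies between 48 − 1 = 47 and 48 + 1 + 13 + 2 = 64. Table 4 anticipates a test-device lifetime of up to nine months, about 39 weeks, so the interval opens about 48 − 39 = 9 weeks later.

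**What else could catch such an event at RT1.**

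- Criterion 1 needs a serious event or one of special interest; criterion 3 needs a visual change or a serious condition.
- Criterion 4 needs an abnormal eye test; criterion 7 needs an infectious, inflammatory, cancerous or pre-cancerous lesion in the treatment area.
- Criterion 9 needs an autoimmune or connective tissue disease, or immuno-modulating therapy.
- Inclusion criterion 4 and Table 16 concern healthy, non-inflamed skin.
- Criterion 19 covers "Any medical condition prohibiting the inclusion for repeat-treatment according to the judgement of the treating investigator", which is discretionary. So are the withdrawal reason for an adverse event in 6.3.6 and the recorded action "device withdrawn [no touch-up treatment(s) / repeat-treatment due to AE" in 14.3.

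A related, non-serious, non-inflammatory nodule or induration that starts after Visit 9 passes every mandatory item unless the skin is judged unhealthy. The decision is then the investigator's. Criteria 11 to 15 also refer to the initial treatment phase, but they are not part of this point: 6.3.9 already prohibits those procedures during the whole investigation.

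**The case against.** The strongest reply is that the phrase can be read loosely as meaning any time before repeat treatment. Criterion 13 divides the study into just two phases, and the explanatory part of criterion 2 lists relationship and outcome but no onset date. A site might well apply it that way. The Glossary nevertheless gives an explicit end point, and 6.3.5.1, 6.3.11 and 6.5.16 treat the screening stage separately, so the literal reading is the better one. Needing a loose reading to reach the sensible result is itself a reason to correct the text.

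A second reply is that other controls leave little uncovered, and that board-certified specialists lead the sites. This largely stands: adverse events are recorded and eligibility is re-assessed at RT1 before injection, and many event types are caught elsewhere. What remains is narrow and depends on judgement, whereas the same event with earlier onset does not.

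A third is that the number affected is unknown. This stands in full. The Protocol gives no rate for such late events, and no share of the approximately 300 expected repeat-treated subjects whose RT1 falls after Visit 9. The nine-month lifetime describes the test device only, yet comparator subjects can also be re-treated. The Protocol does foresee late-onset nodules with dermal fillers (6.2.4.2, in the comparator precautions), but gives neither frequency nor timing.

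**Conclusion.** The point holds and is minor. Under the Protocol's own definitions, criterion 2 leaves an interval of up to 14 weeks nominally before RT1 in which a new related event, if neither serious nor of special interest, is not a mandatory bar to re-injection. The interval is zero for subjects treated at Visit 9. Few subjects are likely to be affected and zero is possible; the number cannot be derived from the document.

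The conclusion rests on the Glossary's phase definitions and, for the 14 weeks, on the Table 3 footnote rather than the 6.5.10 heading. The primary endpoint, sample size and randomised comparison are not affected. Adverse-event start dates are recorded (14.3), so any subject re-injected with such an event can still be identified in reporting.

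**What to change.** In criterion 2 of 6.3.5.2 and in the synopsis, replace the condition on phase and timing so that the criterion covers a related adverse event *with onset at any time since the baseline injection and ongoing at Visit RT1*. Keep the existing lists of relationship and outcome categories. This gives criterion 2 the open look-back that criteria 1 and 3 already have and reduces the uncovered interval to zero. Criteria 11 to 15 need no change; aligning their wording would be optional tidying.

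The cost is a formal amendment under section 9, with signatures from the sponsor, the Coordinating Investigator and the Principal Investigators. It also needs IRB/EC approval and, if applicable, regulatory approval, because a safety eligibility rule changes. The eCRF eligibility text must be updated. No new data are needed, since adverse events are already recorded at SV2 to SV4 and at RT1. A few subjects may no longer qualify for repeat treatment, and only those not yet re-injected would benefit.
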